2.4 Impact of Covariates on the Outcome Variable

For each variable for which the impact has been evaluated, frequency distributions will be given of the impact, for all patients and per level of the outcome variable (treatment choice).

Demographic data

- Age and Weight loss
- Gender, Smoking status, and ECOG
- Patients' preference for treatment choice

Medical history

- Metastatic disease status
- Tumor size diameter and Number of metastatic sites
- Brainmets, Symptomatic/asymptomatic, and Treatment
- Livermets, Concomitant malignancies, Histology, IHC PD-L1, High TMB, and Genetic testing complications

Co-morbidities

- Each Co-morbidity

Auto-immune disease

- Presence and activity of each Auto-immune disease

Current/recent medication

- Use of Corticosteroids and Dose
- Use of Other immunosuppressants and Antibiotics

Prior cancer treatment in earlier stage NSCLC

- Each Prior cancer treatment in earlier stage NSCLC

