9.1 Statistical Methods

The statistical analysis will be performed using SAS software 9.2.

9.1.1 Primary Objective(s): Calculation of Epidemiological Measure(s) of Interest (e.g. descriptive statistics, hazard ratios, incidence rates, test/retest reliability)

Systemic treatment choices and best supportive care are defined as :

- 1) Chemotherapy (chemo)
- 2) Immunotherapy (IO)
- 3) immuno combined therapies (IO+IO)
- 4) IO+chemo
- 5) IO+bevacizumab+chemo (IO+bev+chemo)
- 6) best supportive care (BSC).

Descriptive statistics of the relation between variable category and systemic treatment choice will be provided. The descriptive statistics will involve the number of times (frequency) a variable category is indicated as being linked to a systemic treatment option.

For each of the variable categories that are linked to a systemic treatment choice, descriptive statistics of the underlying variables will be provided. These descriptive statistics will consist of:

- For the quantitative variables, summary statistics including mean, standard deviation, 95% confidence interval on the mean, minimum, first quartile, median, third quartile, maximum, and number of available and number of missing observations.
- For the categorical variables, frequencies and percentages.

In an exploratory analysis, a penalized hierarchical logistic regression model for discrete choices will be used to evaluate the effect of the potential explanatory variables on the 1st line systemic treatment.

9.1.2 Secondary Objective(s): Calculation of Epidemiological Measure(s) of Interest (e.g. hazard ratios, incidence rates, test/retest reliability)

No secondary objectives.

9.1.3 Exploratory Objective(s): Calculation of Epidemiological Measure(s) of Interest (e.g. hazard ratios, incidence rates, test/retest reliability)

Investigate if there are differences in the link between variable categories and systemic treatment choices for the 4 types of sites that are defined.

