9.3 Sample Size and Power Calculations

The study is descriptive and no sample size calculations will be performed. In order to have a representative picture of the pneumo-oncologists' NSCLC systemic treatment decision in Belgium, a minimum of 200 patients need to be enrolled in the study.

A maximum of 10% of the total study population can be enrolled in a site to avoid bias. A minimum of 30 patients need to be included in a subgroup for any given analysis.

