1.8.1 Descriptive Analysis

Throughout this document the following terminology is used for indicating the type of descriptive analysis:

- 'Descriptive statistics' is the description to be provided for quantitative variables, and consists of the mean, standard deviation (SD), 95% confidence interval (CI) on the mean, minimum, 1st quartile, median, 3rd quartile, maximum, number of available observations, and number of missing observations.
- 'Frequency distribution' is the description to be provided for ordinal and nominal variables and consists of numbers and percentages for each of the scores or categories. Exact 95% CIs will be provided for key variables.

The descriptive analysis consists of:

1. Site Characteristics

Descriptive statistics will be provided for the diagnostic volume. Other site characteristics, including the site type, will be described by frequency distributions.

2. Patient Characteristics by Outcome Variable and by Site Type

Descriptive statistics and frequency distributions will be used to describe numerical and ordinal/nominal patient characteristics, respectively. The analysis will be performed for:

- All patients in the EP
- By outcome variable (Chemo+IO, Chemo, IO, BSC)
- By site type (4 subgroups).

Also, frequency distributions of the outcome variable will be given for all patients in the EP and by site type.

3. Impact of Covariates on the Outcome Variable

The impact of variables, as indicated by the investigator, on the outcome variable, is described as one of the following:

- Important impact (variable selected as one of the three most important characteristics)
- Impact (variable indicated as having an impact, but not selected among the three most important characteristics)
- No impact (variable not indicated as having impacted the treatment choice)

For each variable the frequency distribution of the impact is provided per level of the outcome variable (chemo, IO, IO+chemo, and BSC).

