1.8.2 Statistical Modelling

An exploratory analysis will be performed, consisting of a multinomial logistic regression model that assesses the effect of patient characteristics and the site type on the outcome variable.

The previously defined outcome variable has four levels (chemo, IO, IO+chemo and BSC). The level with the highest frequency will be used as the reference in the multinomial logistic model.

Variables considered as predictors in the model are the site type and patient characteristics with less than 20% missing or unknown values. In case of yes/no variables with further conditional questioning (e.g. Inflammatory interstitial lung disease (yes/no) and if yes, Active/non-active) only the yes/no variable is included in the model. Selection of the final model, containing only predictors with a significant effect on the outcome variable, will be done using automatic selection procedures.

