1.9 Deviations from the Analysis Foreseen in the Protocol

The protocol foresaw an exploratory analysis of the outcome variable using a penalized hierarchical logistic regression model for discrete choices.

Since a penalized logistic regression is not available in SAS, it was decided to use the classical multinomial logistic regression approach, with a stepwise selection procedure.

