2.3 Patient Characteristics by Outcome Variable and by Site Type

- Frequency distribution and 95% CI for the outcome variable (treatment choice).
- Frequency distributions and 95% CI for the outcome variable (treatment choice) by site type.

The following descriptive analysis is performed broken down by the outcome variable (all patients in the EP and 4 subgroups), and by site type (4 subgroups):

Demographic data

- Descriptive statistics for Age and Weight loss
- Frequency distributions for Gender, Smoking status, and ECOG
- Frequency distribution for Patients' preference for treatment choice

Medical history

- Frequency distribution for Metastatic disease status
- Descriptive statistics for Tumor size diameter and Number of metastatic sites
- Frequency distributions for Brainmets, Symptomatic/asymptomatic, and Treatment
- Frequency distributions for Livermets, Concomitant malignancies, Histology, IHC PD-L1, High TMB, and Genetic testing complications

Co-morbidities

- Frequency distribution for each Co-morbidity

Auto-immune disease

- Frequency distributions of presence and activity of each Auto-immune disease

Current/recent medication

- Frequency distributions for use of Corticosteroids and for Dose
- Frequency distributions for use of Other immunosuppressants and Antibiotics

Prior cancer treatment in earlier stage NSCLC

- Frequency distribution for each Prior cancer treatment in earlier stage NSCLC

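### Protocol 9.1.3 asks whether the factors linked to treatment choice differ by site type, but no SAP analysis splits the impact ratings by site type and SAP 1.9 does not say so

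*SAP*

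**What the plan says.** **Protocol.** Section 9.1.3 states the exploratory objective: "Investigate if there are differences in the link between variable categories and systemic treatment choices for the 4 types of sites that are defined". Section 9.1.1 says how that link is described: "the number of times (frequency) a variable category is indicated as being linked to a systemic treatment option". Section 9.3 sets a floor for subgroups: "A minimum of 30 patients need to be included in a subgroup for any given analysis".

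**SAP, impact ratings.** Section 1.8.1, item 3, grades each rating as important impact, impact or no impact, and plans: "For each variable the frequency distribution of the impact is provided per level of the outcome variable". Section 2.4 repeats this: "frequency distributions will be given of the impact, for all patients and per level of the outcome variable (treatment choice".

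**SAP, site type.** Section 2.2 describes the sites. Section 2.3 breaks down patient characteristics and treatment by site type, for example "Frequency distributions and 95% CI for the outcome variable (treatment choice) by site type". Sections 1.8.2 and 2.5 enter site type in a "multinomial logistic regression model that assesses the effect of patient characteristics and the site type on the outcome variable".

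**SAP, deviations.** Section 1.9 declares one change, to the regression method: "it was decided to use the classical multinomial logistic regression approach, with a stepwise selection procedure". It mentions neither 9.1.3 nor the rated unit.

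**The concern.** Three questions can be asked about site type: do treatments differ, do patients differ, and do the factors that physicians say drove the choice differ? The SAP covers the first two. Protocol 9.1.3 asks the third. A report that follows the SAP exactly would contain several site-type tables and a site-type term in a model, and could look as if it had dealt with the objective when it had not. Because 1.9 is silent, a reader could not tell whether the objective was dropped on purpose.

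There is a related problem of unit. Protocol 9.1.1 counts categories, while the SAP counts variables. A reader who looks for the category frequencies would find variable frequencies, with no note explaining the change.

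**Working it through.** The plan gives no figure to reproduce: the study is descriptive and has no sample size calculation. The check is a comparison of text, followed by arithmetic on what added tables could show.

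**1. Does any SAP analysis use the ratings by site type?**

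| SAP section | Uses impact ratings? | Uses site type? |
|---|---|---|
| 2.2 site description | No | Yes |
| 2.3 treatment and patient characteristics | No | Yes |
| 1.8.1 item 3 and 2.4 impact tables | Yes | No |
| 1.8.2 and 2.5 model | No | Yes, as a main effect; no interaction listed |

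No row has Yes in both columns. SAP 1.2.1 does not restate 9.1.3, and 1.9 does not declare it dropped.

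**2. Cell sizes.** Inputs: 200 to 210 patients (SAP 1.4), about 21 sites (Protocol 3.2), four site types (SAP 1.6), four observed treatment levels (SAP 1.2.2), minimum of 30 (Protocol 9.3), and a cap of 20 patients per site (SAP 1.3). The documents do not give the split across site types, so equal groups are assumed.

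- Per site type: 210/4 = 52.5; 200/4 = 50. Both exceed 30.
- Per site type and treatment (16 cells): 210/16 = 13.1; 200/16 = 12.5. Both averages are below 30.
- Most cells that can reach 30: 210/30 = 7; 200/30 = 6.67, so 6.
- One treatment compared across all four site types: 4 × 30 = 120 patients, or 57% of 210. Two treatments would need 240, more than the study has.
- A site type made up of a single site cannot reach 30, because the cap is 20.

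**3. Precision by site type, best case.** For two groups of n patients with the same share p, the 95% half-width of the difference is 1.96 × √(2p(1−p)/n), with patients treated as independent.

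- n = 52.5, p = 0.5: 1.96 × √(0.5/52.5) = 19.1 points.
- n = 52.5, p = 0.1: 1.96 × √(0.18/52.5) = 11.5 points before rounding (11.48), so about 11.
- n = 30, p = 0.5: 1.96 × √(0.5/30) = 25.3 points.

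**4. Clustering.** Site type is a property of the site, and the ratings come from the treating physicians there. On average there are 21/4 ≈ 5 sites per type and 210/21 = 10 patients per site. The design effect is 1 + (10 − 1) × ICC. The documents give no ICC, so 0.05 and 0.10 are assumed as a range.

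- ICC 0.05: 1.45; 19.1 × √1.45 = 23.0 points.
- ICC 0.10: 1.90; 19.1 × √1.90 = 26.3 points.

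**5. The rated unit.**

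| Item | Protocol | SAP |
|---|---|---|
| Yes/no rating | Category in 2.1 and at the end of 4.2; covariate at the start of 4.2 | Variable (1.2.1, 1.5.2) |
| Top-three choice | Category (end of 4.2) | Variable (1.5.2) |
| Frequency count | Category (9.1.1) | Variable (1.8.1, 2.4) |

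On the yes/no rating the protocol disagrees with itself, so the SAP has some support. On the top-three choice and the frequency count the protocol names only the category. The top-three categories cannot always be rebuilt from the top-three variables, because all three variables may fall in one category.

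**The case against.** **Site type is already in the model and in 2.3.** True, but a main effect shows whether treatment differs by site type, not whether the reasons do. Suppose one reads the link in 9.1.3 as a statistical association between characteristics and treatment rather than as the ratings. Even then, 2.3 breaks down by treatment and by site type separately, and the model lists no interaction. The gap remains on either reading.

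**The aim is slight.** It is a single sentence in the statistics section; the protocol summary and Section 2 list only the primary objective. This stands, and it limits the weight of the point. It does not explain the silence in 1.9.

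**The added tables cannot fully answer the question.** This also stands. Tables by site type pool the treatments, and most cells within treatment will be too small. It is a reason to state the limit, and to present the tables as descriptive.

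**Applying the minimum of 30 only in 2.4 would be inconsistent.** This is right. The SAP does not carry the Protocol 9.3 rule at all, and 2.3 uses the same site types without it. The rule has to apply in both places.

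**The unit may have been settled in the CRF.** This is possible. SAP 1.1 cites an annotated CRF that is not among the documents, so the level at which ratings were captured cannot be checked.

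A reader might infer from the change of unit that the primary result is lost. The documents do not support that: variable-level ratings by treatment are planned, grouped in 2.4 under the protocol's patient-level category headings. What is shown is an undeclared change, not a missing result.

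**Conclusion.** The gap is confirmed on the text with high confidence: no planned analysis relates the impact ratings to site type, and the objective is not declared as dropped. It should be corrected, but it concerns an exploratory aim and leaves the primary analysis intact.

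What the correction can deliver is modest. Assuming equal groups, about 52 patients per site type gives differences with a margin of about ±19 points for shares near 50% and about ±11 for shares near 10%, if patients are independent. At an assumed ICC of 0.05 to 0.10, ±19 becomes about ±23 to ±26. The actual split may be less favourable: SAP 1.6 halves the sites at the median volume, but the division by trial participation is unknown.

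The change of unit is a secondary point held with moderate confidence. It is clearest for the top-three choice and the frequency count, and weakest for the yes/no rating.

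**What to change.** **SAP 2.4.** Add the impact frequency tables (important, impact, none) by site type, with denominators and the number of sites in each type. Add them by site type within treatment only for cells of at least 30 patients, and state that smaller cells are not analysed. Present all of them as descriptive, with a note on clustering by site and physician.

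**SAP 2.3.** Apply the Protocol 9.3 minimum to the site-type breakdowns in the same way.

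**SAP 1.9.** State that the pooled tables answer 9.1.3 only in part, and why: about 13 patients per cell on average, and at most 7 of 16 cells able to reach 30. If the tables are not produced, state that 9.1.3 is not addressed. Declare also that the top-three choice and the 9.1.1 frequency are reported per variable instead of per category.

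**Unit.** Check it against the annotated CRF, and reconcile the opening of Protocol 4.2 with Protocol 2.1 and the end of 4.2. A table that rolls variables up to categories is optional and is not needed for this fix.

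**Cost.** A few extra tables with some small cells, drawn from ratings that SAP 1.5.2 says are recorded, plus a few sentences of SAP text. The regression model does not change.

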2.5 Exploratory Analysis

The following variables will be considered in a multinomial stepwise logistic regression analysis:

- Site type (4 subgroups)
- Age
- Gender
- Weight loss
- Smoking status (current/former (≥ 1 year)/never)
- ECOG status (0/1/2/3-4)
- Patients' preference for treatment choice (yes/no)
- Metastatic disease status (M1a/M1b/M1c)
- Tumor size diameter
- Number of metastatic sites
- Brainmets (yes/no)
- Livermets (present/not present)
- Concomitant malignancies (present/not present)
- Histology (squamous/non-squamous)
- IHC PD-L1 (PD-L1 TPS $<1\%$ / $1-49\%$ / $\geq 50\%$)
- High TMB (present/not present)
- Genetic testing complications (turn-around time/biopsy availability)
- Each co-morbidity (yes/no)
- Each auto-immune disease (yes/no)
- Use of corticosteroids, other immunosuppressants, and antibiotics (yes/no)
- Use of each prior cancer treatment in earlier stage NSCLC (yes/no)

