1.5.2 Patient Characteristics

After making the treatment choice, the investigator records the following variables and indicates whether the characteristic impacted the treatment choice (yes/no). Of the variables indicated as having an impact, the investigator chooses at least one and a maximum of three most important characteristics.

Demographic data

- Age (years)
- Gender (male/female)
- Weight loss (%)
- Smoking status (current/former (≥ 1 year)/never/unknown¹)
- ECOG status (0/1/2/3-4/unknown¹)
- Patients' preference for treatment choice (yes/no/unknown¹)

Medical history

- Metastatic disease status (M1a/M1b/M1c/unknown¹)
- Tumor burden:
 - Tumor size diameter (mm)
 - Number of metastatic sites
- Brainmets (yes/no), if yes:
 - Symptomatic/asymptomatic
 - Treated with SRT/treated with WBRT/not treated
- Livermets (present/not present/unknown¹)
- Concomitant malignancies (present/not present/unknown¹)
- Histology (squamous/non-squamous/not otherwise specified¹)
- IHC PD-L1 (PD-L1 TPS $< 1\%$ / $1-49\%$ / $\geq 50\%$ / unknown¹)
- High TMB (≥ 10 mutations/Mb) (present/not present/unknown¹)
- Genetic testing complications (turnaround time/biopsy availability/not tested¹/not applicable¹)

Co-morbidities

Presence (yes/no) of the following diseases:

- Myocardial infarction in the last year
- Congestive heart failure
- Peripheral vascular disease
- Hypertension
- Cerebrovascular event in the last year
- Transient ischemic attack in the last year
- Diabetes with complications
- Renal disease
- Liver disease
- Hematological disease
- Chronic obstructive pulmonary disease
- Chronic infections
- Mental disorders

¹ Considered missing in the analysis

Autoimmune disease

Presence, and in case present, active (yes/no), of the following diseases:

- Inflammatory interstitial lung disease
- Inflammatory bowel disease (IBD)
- Inflammatory joint disease
- Psoriasis
- Connective tissue disease

Current/recent medication

- Corticosteroids (yes/no), and if yes, low dose/high dose (≥ 10 mg/day Prednisolone or equivalent)
- Other immunosuppressants
- Antibiotics

Prior cancer treatment in earlier stage NSCLC

Did the patient undergo the following treatment (yes/no) and if yes, the year of the treatment:

- Single-modality treatment
- Multi-modality treatment
- Surgery/radiotherapy
- Previous IO treatment

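### Two recorded genetic-testing answers are coded as missing, so the exploratory model cannot show whether a testing complication, or not being tested, is associated with treatment choice

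*SAP*

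**What the plan says.** SAP 1.5.2 lists the variable as "Genetic testing complications (turnaround time/biopsy availability/not tested", followed by a fourth level, not applicable. The last two levels carry footnote 1, which reads "Considered missing in the analysis". SAP 2.5 follows this and lists the candidate predictor as "Genetic testing complications (turn-around time/biopsy availability", with no third or fourth level.

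SAP 1.8.2 sets the entry rule: "Variables considered as predictors in the model are the site type and patient characteristics with less than 20% missing or unknown values". The SAP does not say how a patient with a missing predictor value is handled in the fit. SAP 1.9 replaces the protocol's penalised hierarchical model with an ordinary multinomial logistic regression and stepwise selection.

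Histology is treated in the same way. SAP 1.5.2 lists "Histology (squamous/non-squamous/not otherwise specified" with the footnote on the last level, and SAP 2.5 models "Histology (squamous/non-squamous". Protocol 4.2 includes both NOS and not tested among the values to be recorded.

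**The concern.** On most of the variables that carry the footnote, it marks an unknown value, which is a genuine gap in the data. Not tested and not applicable are different: the investigator has given an answer. Coding them as missing has two effects.

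- They count against the variable under the 20% rule, so the variable may be excluded because patients had no listed complication, not because data are absent.
- If the variable survives, the patients needed as a comparison group have no level in it.

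The study asks how patient, tumor and site characteristics relate to treatment choice. For genetic testing the natural questions are whether a delay or a lack of biopsy material goes with a different choice, and whether not testing does. This model is the only planned analysis that relates the characteristics jointly to treatment choice, and as coded it cannot address either question.

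**Working it through.** The plan states no figure for this point, so there is none to reproduce. The check applies the SAP's own rule to its own level lists.

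**Inputs.** N = 200 to 210 (SAP 1.4). Entry requires a missing share below 0.20 (SAP 1.8.2). Not tested and not applicable count as missing (SAP 1.5.2, footnote 1). The outcome has four levels (SAP 1.2.2), so each predictor degree of freedom (df) costs 4 − 1 = 3 parameters.

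**Step 1: entry threshold.** Find the largest m with m/N < 0.20.
- N = 210: 0.20 × 210 = 42, so m ≤ 41. At least 210 − 41 = 169 patients (80.5%) must have turnaround time or biopsy availability recorded.
- N = 200: 0.20 × 200 = 40, so m ≤ 39. At least 200 − 39 = 161 patients (80.5%) must.

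**Step 2: what happens at different complication shares.** The documents do not give this share, so the values below are assumptions, with no other missing values.
- 10%, 30%, 50% or 80%: dropped. At 80% of 210, 42 are coded missing, which is exactly 20% and not below it.
- 85%: enters, with about 178 of 210 (170 of 200) patients having a value.
- 90%: enters, with 189 of 210 (180 of 200).

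**Step 3: what the term estimates if it enters.** It has two levels, both complications, hence one df. The only contrast is turnaround time against biopsy availability. Patients coded missing would also leave a complete-case fit. That is the usual default, assumed here because the SAP states no rule.

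**Step 4: cost of using the four recorded levels.** This takes the answers as mutually exclusive.
- Candidate df in SAP 2.5: 24 for the 17 individually named variables, 13 co-morbidities, 5 autoimmune diseases, 3 medications and 4 prior treatments. The total is 49 df over 42 predictors.
- As planned: 49 × 3 + 3 intercepts = 150 parameters.
- Genetic testing on four levels (3 df instead of 1): 51 × 3 + 3 = 156, which is 6 more.
- If the term would otherwise be excluded: 48 × 3 + 3 = 147, so 156 is 9 more.
- With the two complications merged (three levels, 2 df): 50 × 3 + 3 = 153, which is 3 more than 150 or 6 more than 147.

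**Histology NOS.** Its share is not given. At an assumed 5%, 10% or 15% of 210, about 11, 21 or 32 patients would have no histology value. At 5%, 10.5 patients over four outcomes is about 2.6 per outcome.

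**The case against.** The best defence is that SAP 2.5 lists variables to be considered, so screening one out is planned behaviour. That is true, but here the screen removes the variable because of answers that were given.

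A second objection is that the main gain depends on what not applicable means, and only the annotated CRF can settle that. This stands, and the fix is conditional on it. Protocol 1.1 ties molecular testing to nonsquamous disease, so the level could mean that testing was not indicated. Recovering not tested as a level does not depend on this.

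A third is that the model is already heavily parameterised and no longer penalised. This also stands, and it is why merging sparse levels should be allowed.

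A reader might go further in three directions that the documents do not support:

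- *That the model will in fact compare one complication with the other.* This happens only if the variable passes the 20% rule, and the counts are not given.
- *That NOS must have its own level in the model.* Protocol 1.1 describes NOS partly as a residual class, and the treatment algorithm there has only squamous and non-squamous rows. At the assumed shares of 5% and 10%, NOS falls below the 30 patients that Protocol 9.3 requires for a subgroup, although it is open whether a covariate level counts as one. Leaving NOS out of the model is a defensible trade-off.
- *That the descriptive tables hide these levels.* SAP 2.3 plans "Frequency distributions for Livermets, Concomitant malignancies, Histology, IHC PD-L1, High TMB, and Genetic testing complications", and SAP 1.8.1 says that a frequency distribution "consists of numbers and percentages for each of the scores or categories". The footnote leaves some doubt about display, but no omission is shown.

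**Conclusion.** The point holds for the genetic-testing predictor and is minor. The predictor is either screened out, unless at least 169 of 210 (161 of 200) patients had one of the two complications, or it enters with the single contrast of one complication against the other. The conclusion does not depend on which of these occurs: neither allows a comparison with untested patients or with patients who had no complication. The thresholds follow from the SAP's rule alone. The complication share, the NOS share and the meaning of not applicable are not in the documents.

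The effect is confined to the exploratory model. The individual listings (SAP 1.8) and the investigator-rated impact tables (SAP 2.4) are unaffected. For histology NOS, the documents support asking for the count to be reported, and no more than that.

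**What to change.** 1. In SAP 1.5.2, remove footnote 1 from not tested and not applicable, and state that neither counts as missing under the SAP 1.8.2 rule.
2. In SAP 2.5, enter the variable on its recorded levels: turnaround time, biopsy availability, not tested and not applicable. Use not applicable as the reference only if the CRF confirms that it means no complication. Otherwise label it as its own level and state that complication versus none cannot be estimated.
3. State before the fit that, if levels are sparse, turnaround time and biopsy availability are merged into one any-complication level, and give the count that triggers this.
4. Optional: report the NOS count by treatment choice and the N entering the model, and record whether NOS is modelled separately.

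The cost is SAP wording and recoding, as every level is already collected. The statistical price is 6 more parameters (9 if the term would otherwise be excluded) on about 150 candidates for at most 210 patients, or 3 (6) with the two complications merged. Merging gives up the contrast between the two complications.
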